3.8 Combination RP -3500 and Ola parib Shows Preclinical Efficacy and Synergy

Using an isogenic DLD1 colorectal cancer cell line system, combination RP-3500 and olaparib at sub-lethal doses was profoundly cytotoxic to breast cancer type 2 susceptibility protein-knockout (BRCA2-KO) cells, while minimally affecting the viability of wild type (WT) cells (after 8 or 6 days

а

of treatment, respectively) (Figure 4A). The combination also showed a strong synergistic effect on viability at markedly lower concentrations in BRCA2-KO cells than WT (Figure 4B).

#### Figure 4. BRCA2-deficient cells are sensitive to RP-3500 and olaparib.

Abbreviations: BRCA2 = breast cancer type 2 susceptibility protein; BRCA2-KO = breast cancer type 2 susceptibility protein-knockout; SD = standard deviation; WT = wild type a. When combined, sub-lethal doses of RP-3500 and olaparib eliminate BRCA2-deficient cells. DLD1 WT and

[figure not shown]
# 3.9 Intermittent Dosing of Comb ination RP -3500 and Olaparib Is Equally Efficacious as Continuous Dosing

In the same DLD1 BRCA2-KO cell model, reducing the treatment time of combination RP-3500 and olaparib to 3 days followed by removal of the compounds for 5 days was equally as efficacious in killing BRCA2-KO cells as 8 days of continuous treatment (Figure 5A). These findings were confirmed using a different cell model of SUM149PT, which are BRCA1-mutated triple negative breast cancer cells. Intermittent dosing of the drug combination (3 days on 5 days off) produced equal efficacy as compared to continuous 8 day dosing and increased efficacy as compared to sequential dosing (i.e. olaparib treatment for 3 days alone followed by RP-3500 treatment for 3 days alone followed by 2 days off) (Figure 5B). These findings support intermittent dosing of the drug combination.

Figure 5. Intermittent dosing of combination RP-3500 and olaparib produced equal efficacy as compared to continuous and sequential dosing.

A) DLD1 BRCA2-KO and B) SUM149PT (BRCA1-mutated triple negative breast cancer) cell models

[figure not shown]

3.10 Combination RP-3500 and Ola parib is More Efficacious at Reduced Doses than RP - 3500 Monotherapy at Higher Doses

Dosing strategies for combination RP-3500 and olaparib were explored in SUM149PT xenograft mice models. Concomitant administration of RP-3500 with olaparib for 3 days weekly resulted in higher efficacy than sequential administration (Figure 6). Furthermore, intermittent administration of RP-3500 and olaparib was well tolerated with <5% body weight loss over the course of the experiment compared to continuous concomitant dosing schedules (data not shown). The olaparib doses selected in this study represent exposure levels of ~11  $\mu$ M, which is comparable to ~40% of the circulating free drug exposure levels of olaparib at steady state in humans taking 300 mg BID daily. This dose is less than the maximum tolerated dose (MTD) of 400mg BID as previously determined. However, prior pharmacokinetic and efficacy data comparing 200mg BID versus 400mg BID in phase I and phase II trials have not shown major differences between the two dosing strategies. Notably, the lower dose of 200mg BID led to decreased grade 3-4 anemia of 6% as compared to 13% in patients treated with 400mg BID.

Figure 6. Efficacy of intermittent sequential versus concomitant RP-3500 plus olaparib in the SUM149PT breast cancer xenograft model (BRCA1-deficient),

Abbreviations: BID = twice daily; *BRCA1* = breast cancer type 1 susceptibility protein; MC = methylcellulose; NOD-SCID = non-obese diabetic severe combined immunodeficiency; PO = oral; QD = once daily; SEM = standard error of measure; SLS = sodium lauryl sulfate

Tumor xenograft volume in mice treated with RP-3500 (QD) and olaparib (BID) PO 3 days weekly (either concomitant or sequential). Olaparib was administered on Days 1-3 weekly and RP-3500 Days 1-3 in all groups except the sequential schedule where RP-3500 was administered on Days 4-6; treatment lasted for 5 weeks (Day 35) for all groups. Olaparib and RP-3500 were administered as suspensions in 0.5% MC/0.02% SLS. Results are expressed as mean  $\pm$  SEM, N=9/group in female NOD-SCID mice.

RP-3500 at 15 mg/kg is 50% of the MTD on a 3 day on/4 day off dosing schedule. The combination of low dose RP-3500 administered concomitantly with low dose olaparib given on an intermittent schedule led to superior efficacy when compared to either single agent at full dose (Figure 6).

#### 3.11 Rationale for Starting Doses of RP -3500 and Olaparib

The currently presented data supports the administration of RP-3500 and olaparib with intermittent dosing (3 days per week) and at reduced doses from the previously determined monotherapy MTDs. Furthermore, dosages of RP-3500 and olaparib must also account for the potential drug-drug interaction between RP-3500 and olaparib as previous in vitro data has shown olaparib to be an inhibitor of the two major metabolic proteins for RP-3500, including CYP3A4 and UGT1A1. Therefore, the proposed starting dose of RP-3500 at 50mg daily and olaparib at 100mg BID administered with intermittent 2 days per week dosing was based on preclinical PK data and prior toxicity experience with both drugs to help reduce toxicity while maintaining efficacy.

3.12 Rational e for Allowing Creatinine Clearance (CrCl) Between 45 and 59 mL/min

In an analysis of 154 solid tumor patients treated with RP-3500, there were small changes in the PK clearance of RP-3500 among patients with normal renal function (N=62), mild renal impairment (N=49) and moderate renal impairment (N=13) defined as CrCl between 45 and 59 mL/min (Table 3). However, the analysis is confounded by the lower mean body weights in the moderate renal impaired patients, but still supports little effect of renal impairment on the PK of RP-3500.

	Normal (N=61)	Mild (N-49)	Moderate (45-59 ml/min) (N=13)	Moderate (<45 ml/min) (N=4)	Missing (N=7)	Overall (N=134)
Weight (kg)						
Mean (SD)	85.6 (19.9)	68.7 (14.5)	65.5 (13.7)	52.8 (6.94)	NA (NA)	76.0 (19.5)
Median [Min, Max]	85.2 [53.1, 148]	66.9 [45.0, 113]	61.4 [50.3, 97.9]	53.9 [44.5, 58.9]	NA [NA, NA]	76.5 [44.5, 148]
Missing	0 (0%)	0 (0%)	0 (0%)	0 (0%)	7 (100%)	7 (5.2%)
Dose Normalized AUC 0-655 of RP-3500 (ng.h/mL/mg)						
Mean (SD)	168 (78.6)	180 (69.3)	221 (88.3)	239 (63.2)	180 (86.8)	180 (77.4)
Median [Min, Max]	154 [66.6, 554]	158 [66.6, 373]	190 [107, 435]	225 [179, 325]	156 [93.2, 353]	163 [66.6, 554]
Dose Normalized AUC 0-12,05 of RP-3500 (ng.h/mL/mg)						
Mean (SD)	237 (129)	253 (112)	318 (148)	328 (100)	252 (136)	254 (126)
Median [Min, Max]	220 [75.6, 905]	227 [75.4, 597]	268 [132, 678]	299 [241, 471]	227 [112, 522]	227 [75.4, 905]
Dose Normalized Cmax.m of RP-3500 (ng/mL/mg)						
Mean (SD)	49.1 (17.1)	54.2 (16.9)	63.7 (17.5)	71.8 (15.9)	54.6 (17.6)	53.3 (17.6)
Median [Min, Max]	47.0 [19.0, 117]	52.6 [26.9, 87.2]	61.8 [39.5, 104]	72.0 [55.0, 88.1]	54.0 [32.0, 90.0]	50.8 [19.0, 117]
Dose Normalized Cmin,st of RP-3500 (ng/mL/mg)						
Mean (SD)	3.04 (5.62)	3.88 (4.89)	4.38 (3.67)	3.94 (2.91)	4.52 (6.82)	3.58 (5.17)
Median [Min, Max]	1.65 [0.157, 43.7]	2.67 [0.189, 21.5]	3.80 [0.736, 13.5]	2.83 [1.86, 8.26]	2.22 [0.519, 19.8]	2.11 [0.157, 43.7]
Daily Dose Normalized AUC21d of RP-3500 (ng.h/mL/mg)						
Mean (SD)	115 (67.6)	128 (87.7)	154 (75.2)	135 (76.4)	116 (58.3)	124 (76.0)
Median [Min, Max]	98.8 [30.6, 345]	115 [30.2, 565]	162 [56.7, 263]	101 [89.7, 249]	108 [47.1, 201]	108 [30.2, 565]
Daily Dose Normalized Cave of RP-3500 (ng/mL/mg)						
Mean (SD)	5.46 (3.22)	6.10 (4.18)	7.34 (3.58)	6.43 (3.64)	5.53 (2.78)	5.91 (3.62)
Median [Min, Max]	4.71 [1.46, 16.4]	5.46 [1.44, 26.9]	7.72 [2.70, 12.5]	4.80 [4.27, 11.9]	5.12 [2.24, 9.57]	5.14 [1.44, 26.9]

Table 3. PK Clearance of RP-3500 Among Patients with Normal, Mild, and Moderate Renal Impairment

Reassuringly, the modest PK effects of renal impairment did not translate to increased observed toxicities including anemia, neutropenia and treatment-emergent significant adverse events (TESAE) (Table 4,

Table 5, Table 6)

 Table 4. Summary Anemia by Renal Function Categories (CrCL)

	Normal	Mild	Moderate (45-59 ml/min)	Moderate (<45 ml/min)	Missing	Overall
	(N=61)	(N=49)	(N=13)	(N=4)	(N=7)	(N=134)
Adverse Event						
No Anaemia	23 (37.7%)	10 (20.4%)	2 (15.4%)	0 (0%)	2 (28.6%)	37 (27.6%)
Anaemia	38 (62.3%)	39 (79.6%)	11 (84.6%)	4 (100%)	5 (71.4%)	97 (72.4%)

#### Table 5. Summary Neutropenia by Renal Function Categories (CrCL)

	Normal	Mild	Moderate (45-59 ml/min)	Moderate (<45 ml/min)	Missing	Overall
	(N=61)	(N=49)	(N=13)	(N=4)	(N=7)	(N=134)
Adverse Event						
No Neutropenia	47 (77.0%)	35 (71.4%)	9 (69.2%)	2 (50.0%)	4 (57.1%)	97 (72.4%)
Neutropenia	14 (23.0%)	14 (28.6%)	4 (30.8%)	2 (50.0%)	3 (42.9%)	37 (27.6%)

#### Table 6. Summary TESAE by Renal Function Categories (CrCL)

	Normal	Mild	Moderate (45-59 ml/min)	Moderate (<45 ml/min)	Missing	Overall
	(N=61)	(N=49)	(N=13)	(N=4)	(N=7)	(N=134)
Adverse Event						
No TESAE	47 (77.0%)	35 (71.4%)	9 (69.2%)	2 (50.0%)	4 (57.1%)	97 (72.4%)
TESAE	14 (23.0%)	14 (28.6%)	4 (30.8%)	2 (50.0%)	3 (42.9%)	37 (27.6%)

While Olaparib is affected by CrCl, the package insert for olaparib does not recommend any dose modifications for CrCl between 51-80 mL/min. If a patient has moderate renal impairment, defined as CrCl 31-50mL/min, the package insert recommendation is to decrease Olaparib to 200mg BID. However, due to the anticipated synergy between RP-3500 and Olaparib, the starting dose of Olaparib for this trial is 100mg BID at dose level 1 with a maximum dose of Olaparib at 150mg BID for dose levels 2 and 3, which are all below the recommended reduced 200mg BID for moderate renal impairment.

#### 4 STUDY DESIGN

This is an open-label, multicenter, phase Ib/II study of the combination of camonsertib (RP-3500) and olaparib in R/R CLL patients with DDR deficiencies.

4.1 Justification for New Dosing Schema and Dose Escalation

At the previous dose level 1, five R/R CLL patients were treated with camonsertib (RP-3500) 40mg daily and olaparib 100mg BID dosed 3 days per week. One patient met the definition of a dose limiting toxicity due to persistent grade 4 thrombocytopenia lasting  $\geq$ 7 days. Cytopenias were the most common AEs with 2/5 (40%) of patients experiencing grade 4 thrombocytopenia as per the iwCLL criteria. Grade  $\geq$ 3 neutropenia occurred in 2/5 (40%) of patients with one patient experiencing a grade 3 neutropenic fever outside of the DLT window.

In the ongoing parallel ATTACC study (NCT04972110) of combination camonsertib (RP-3500) and PARPi combinations (either niraparib or olaparib) in patients with molecularly selected cancers (i.e. DDR-deficient solid tumors), similar cytopenias were observed with the 3 days per week dosing. However, better tolerance of the combination was observed when patients were dosed only 2 days per week. In preliminary data, reduction of the dosing to 2 days per week significantly reduced ≥grade 3 toxicities by 5-fold as compared to 3 days per week dosing at similar dosages of combination RP-3500 and olaparib. The 2/5 (i.e. 2 days on and 5 days off) dosing strategy is supported by previous preclinical data generated in DDR-deficient bladder cancer cell lines in which shortening the treatment of the cells to 48 hours had no significant effect on the IC50 as compared to continuous dosing (Refer to RP-3500 Investigator Brochure Section 4.2.1.4.2.1). Furthermore, treating various DDR-deficient solid tumor cell lines with RP-3500 and various PARPi dosed with a 2/5 strategy in vitro demonstrated strong synergy with the combination treatments (Refer to RP-3500 Investigator Brochure Section 4.2.1.5.1). Given the prior clinical experience of RP-3500 and olaparib with the 2/5 dosing strategy in solid tumor patients along with the existing preclinical data to support this dosing method, we propose to amend the phase Ib of combination RP-3500 and olaparib in R/R CLL patients to be dosed with a 2/5 treatment strategy to improve the tolerability of the combination.

## 4.2.2 Dose Escalation

During dose escalation, four DLs of combination therapy of RP-3500 and olaparib may be explored (Table 7. Dose levels of RP-3500 and olaparib in phase Ib portion of the trial.). Subjects will be enrolled in cohorts of three starting with DL 1. Enrollment will be placed on hold to allow for all members of a cohort to complete the Dose Limiting Toxicity (DLT) period. Once all subjects in a cohort have completed the defined DLT evaluation period, the assignment of the dose level for the following cohort will follow the decision algorithm in Table 8. Dose escalation rules according to the keyboard phase I design. Doses may be escalated (E) to the next highest dose level, de-escalated (D) to a lower dose level, or stay (S) at the same dose level (Table 8. Dose escalation rules according to the keyboard phase I design.).

Table 7. Dose levels of RP-3500 and olaparib in phase Ib portion of the trial.

Dose Level	RP-3500	Olaparib
-1#	40mg daily	100mg BID
1*	50mg daily	100mg BID
2*	80mg daily	100mg BID
3*	80mg daily	150mg BID

As long as there are not any unacceptably (U) high toxicities encountered with the enrolled patients as according to the keyboard algorithm, then the trial can continue enrollment in cohorts of 3 patients. Each cohort will complete the DLT window at which point it will trigger the Data Safety Monitoring Committee (DSMC) and the Principal Investigator of the trial to convene and determine the appropriate DL for the following cohort(s). The DSMC and Principal Investigator can also make the recommendation to enroll in cohorts of 1-2 patients if a slower enrollment is required to ensure the safety of the drug combination. All patients enrolled in these smaller cohorts must complete the DLT window prior to the determination of the number of patients to enroll in the next cohort and at which DL. Should a DL accumulate enough DLTs so that the keyboard algorithm dictates a U, the remaining cohorts will be de-escalated to the next lowest DL and no more patients will be treated at the DL with U toxicities.

Table 8. Dose escalation rules according to the keyboard phase I design.

Depending on the number of patients treated on the current dose level and the number of doselimiting toxicities encountered, the algorithm will dictate dose escalation (E) to the next highest dose, de-escalation (D) to the next lowest dose or stay (S) at the current dose level. Should any DL encounter an unacceptable (U) toxicity in the decision table, future cohorts will be D to next lowest dose and no further patients will be treated at this DL.

# 4.2.3 Determination of The MTD and RP2D

After successful enrollment of 18 patients who have completed the DLT window, then the phase Ib portion of the trial will be complete. An exception to this is if any DL enrolls 12 patients and the keyboard algorithm dictates to stay at the current dose level. The MTD and RP2D will be determined to be the DL in which the 12 patients are enrolled as the chances of additional patients treated at the current DL altering the decision table of the keyboard design would be low. Therefore, the phase Ib portion of the trial may be completed before the enrollment of 18 total patients. If a DL reaches 8 patients and 2 DLTs are noted, the keyboard decision table dictates an S at the current DL. The Principal Investigator or DSMC can determine to enroll 4 additional patients at the current DL if the 4 additional patients do not put the total number of patients enrolled into the phase Ib portion over 18.

After the phase lb portion is completed, final DLT rates at each dose level will be estimated by isotonic regression. The weighted least squares regression model will assume monotonic nondecreasing DLT rates with increasing dose and use the empirical (observed) DLT rates at each DL as responses and DL sample sizes as weights, along with the pool adjacent violators algorithm (PAVA) to estimate the DLT rate at each dose level. Given the DLT estimates for each dose level, all tried dose levels that have not been previously declared to be unsafe with a U decision according to the keyboard decision table will be considered for the RP2D. With this constraint, the MTD will be determined as the dose level with the DLT estimate closest to the target toxicity

			Numb	oer of I	Patien	ts Trea	ated A	t Curr	ent Do	ose Le	vel		
# of DLTs Observed	0	1	2	3	4	5	6	7	8	9	10	11	12
0	S	Е	Е	Е	Е	Е	Е	Е	Е	Е	Е	Е	Е
1		D	D	D	S	Е	Е	Е	Е	Е	Е	Е	Е
2			D	D	D	D	D	S	S	Е	Е	Е	Е
3				U	U	D	D	D	D	D	S	S	S
4					U	U	U	D	D	D	D	D	D
5						U	U	U	U	U	D	D	D
6							U	U	U	U	U	U	D
7+								U	U	U	U	U	U
level of 30%.													

Each dose level may enroll approximately 3 to 12 subjects in order to further inform RP2D decision. Enrollment to the highest open dose level will be prioritized if multiple dose levels are open for enrollment. The RP2D will be selected with approval from all investigators and the DSMC after considering the cumulative safety, PK/Pd (as available) and efficacy data from subjects treated in dose escalation.

### 4.2.4 Definition of Dose Limiting Toxicities

DLTs will be assessed for each patient within the DLT window. The DLT window is defined as the time from Cycle 1 Day 1 to Cycle 1 Day 21. Common terminology criteria for adverse events (CTCAE) v5.0 will be used to grade all adverse events (AE) and to provide management guidelines for administrational toxicity. Any of the following AEs which cannot be incontrovertibly attributed to CLL or CLL disease progression will be defined as a DLT.

#### General

- a. Treatment delays > 21 days.
- b. Any grade 5 event.

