#### Hematologic

- a. For patients with baseline/screening absolute neutrophil count (ANC) ≥1000/mm^3, grade 4 neutropenia [ANC <500/mm^3] not responsive to optimal supportive care or G-CSF administration lasting ≥5 days. For patients with baseline/screening ANC <1000/mm^3, DLT here is defined as a ≥75% reduction from baseline ANC not responsive to optimal supportive care or G-CSF administration lasting ≥5 days.
- b. Any grade febrile neutropenia.

- c. For patients with baseline/screening platelet count ≥100,000/mm^3, grade 4 thrombocytopenia (platelet count <25,000/mm^3) lasting ≥7 days. For patients with baseline/screening platelet count <100,000/mm^3, DLT here is defined as a ≥75% reduction from baseline platelet counts lasting for ≥7 days.
- d. Grade  $\geq$ 3 thrombocytopenia-associated bleeding.

Subjects will be considered eligible for DLT assessment if they have received at least 1 dose of RP-3500 and 1 dose of olaparib.

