### 6.6.3 Hematologic and Infectious Toxicities

Optimal supportive care should be offered to the patient in order to mitigate toxicities. Where appropriate, this includes administration of G-CSF, GM-CSF and blood/platelet transfusions as per institutional guidelines. At the start of each cycle, hold therapy until ANC  $\geq$ 500/mm^3 and platelet count is  $\geq$ 25,000/mm^3. Lymphopenia is an expected toxicity of CLL treatments and therefore should be graded and recorded as per CTCAE v5.0, but treatment holds and dose changes are not needed.

This study will utilize the 2018 IWCLL grading scale for hematologic adverse events in patients with baseline platelet count <100,000/mm^3 and/or baseline hemoglobin less than the lower limit of normal. Grading of ANC is at the nadir within the cycle, and patients who have an ANC <1 x  $10^{9}$ /L before therapy will not be evaluable for toxicity. These criteria account for baseline cytopenias secondary to CLL and are detailed in Table 12 below.

Grade	Decrease in platelets or hemoglobin from baseline value, %	Absolute neutrophil count* (nadir) x 10  /L
0	No change to 10	≥2
1	11-24	≥1 and <2
2	25-49	≥1 and <1
3	50-74	≥0.5 and <1
4	≥75	<0.5

Table 12. iwCLL Hematologic Grading

\*If the absolute neutrophil count (ANC) reaches  $<1 \times 10^{9}$ /L, it should be judged to be grade 3 toxicity. Other decreases in the white blood cell count or in circulating granulocytes are not to be considered because a decrease in the white blood cell count is a desired therapeutic end point. A gradual decrease in granulocytes is not a reliable index in CLL for stepwise grading of toxicity. If the ANC was  $<1 \times 10^{9}$ /L before therapy, the patient is not evaluable for toxicity referable to the ANC. The use of G-CSF is irrelevant for the grading of toxicity, but should be documented.

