# 7.6.3 Pharmacokinetic Studies

Plasma samples will be collected at defined time points in section 1.5.1 to assess the pharmacokinetics of RP-3500 and olaparib.

7.6.3.1 On C1D1 and C1D15, blood samples will be collected at pre-dose and 0.5, 1, 2, 4, and 24 hours post dose. Patients will take their doses of RP-3500 and olaparib in the infusion room or clinic after the pre-dose PK blood draw has occurred and at the instruction of the research team. For the 24 hour post dose collection, patients will have PK study blood drawn prior to taking their C1D2 and C1D16 drug doses.

7.6.3.2 On C1D8, blood samples will be collected at pre-dose, 0.5, 1, 2, and 4 hours post dose. Patients will take their doses of RP-3500 and olaparib in the infusion room or clinic after the pre-dose PK blood draw has occurred and at the instruction of the research team.

Blood samples will be processed to plasma and RP-3500 and olaparib will be analyzed by validated LC/MS-MS bioanalytical methods. PK parameters for RP-3500 and olaparib will be calculated using non-compartmental analysis: area under the concentration-time curve (AUC) from time 0 to last quantifiable concentration (AUC0-last); AUC from time 0 to infinity (AUC0-inf); maximum observed plasma concentration ( $C_{max}$ ); time to reach Cmax ( $T_{max}$ ) and terminal elimination half-life ( $t_{1/2}$ ). The effect of olaparib on the AUC0-last and AUC0-inf and Cmax of RP-3500 will be compared to respective monotherapy doses from other studies performed with RP-3500. RP-3500 and olaparib may also be analyzed using population PK methods.

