# 9.2.1 DLT Evaluable Population

For dose-finding, subjects who receive at least one dose of any study drug during the DLT evaluation period will be considered evaluable for a DLT event. Only subjects who have experienced a DLT event or received 80% of the expected doses during the DLT period will be included when evaluating dose level changes.

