# 9.3 Stopping Rules

The trial will be evaluated quarterly for excess toxicity. A rate of 20% grade 3 or higher non-hematological toxicity is acceptable, while a rate of 35% is unacceptable. Stopping boundaries were calculated using the R function "toxbdry" in the package "clinfun". The trial will be stopped if more than 2/4, 3/8, 4/12, 5/16, 6/20, 7/24, 8/28 or 9/34 patients experience grade 3 or higher non-hematologic adverse events attributed to study therapy during the 12 month evaluation period.

The operating characteristics of the stopping rule are difficult to determine precisely because up to 12 patients from the phase Ib portion will contribute to the phase II. We evaluated the operating characteristics in two ways. First, we present operating characteristics of the stopping rule calculated by toxbdry(0.16, 0.4, c(4,8,12,16,20,24,28,34),cP0=0.1, cP1=0.9, ngrid=7) in Table 20. This table assumes the operating characteristics are unaffected by the patients carried over from phase Ib to phase II. Second, we explore the effect of the rollover from phase Ib to phase II. Second, we explore the effect of the rollover from phase Ib to phase II with a scenario in which the dose selection has a relatively large effect (Table 21). There are 3 assumptions: 1) 12 patients from the phase Ib portion contribute to phase II, 2) all of the grade 3 or higher non-hematologic toxicity occurred in the 28 day DLT period of phase Ib, and 3) the observed toxicity in the 12 rollover patients is in the target range of 25-35%. It is noted that the stopping probability in Table 21 is higher than the corresponding stopping probability in Table 20 when the true toxicity is lower than the target, and lower when the true toxicity is higher than the target.

Operating Characteristics of Stopping Rule Calculated by toxbdry			
Probability of DLT	Probability of Crossing Boundary	Probability of Stopping Before Last Patient	Expected Sample Size
0.16	8.9%	7.9%	32.3
0.20	21.1%	18.0%	30.4
0.24	38.9%	32.8%	27.6
0.28	58.4%	50.1%	24.1
0.32	75.5%	66.7%	20.5
0.36	87.6%	80.2%	17.2
0.40	94.6%	89.6%	14.3

Table 20: Operating C haracteristics of Stopping Rule from toxbdry (N = 34)

Table 21: Operating Characteristics of Stopping Rule Under Scenario (N = 34)

Operating Characteristics of Stopping Rule under the Scenario Described Above

Probability of DLT	Probability of Crossing Boundary	Probability of Stopping Before Last Patient
0.16	13.7%	11.3%
0.20	26.3%	20.7%
0.24	41.9%	32.9%

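### The DLT criterion for a treatment delay of more than 21 days cannot be met by the end of the 21-day DLT window, when the cohort decision is triggered; a smaller point is which analyses include the five earlier patients

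*Combined protocol and SAP*

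**What the plan says.** - Section 4.2.4, under General, names "Treatment delays > 21 days" as a DLT. The same section fixes the period: "The DLT window is defined as the time from Cycle 1 Day 1 to Cycle 1 Day 21".
- Section 4.2.2 ties the decision to the end of that period: "Once all subjects in a cohort have completed the defined DLT evaluation period, the assignment of the dose level" for the next cohort then follows Table 8.
- Section 9.3 gives another length. One assumption behind Table 21 is that "all of the grade 3 or higher non-hematologic toxicity occurred in the 28 day DLT period of phase Ib".
- Section 9.2.1 restricts who counts: "Only subjects who have experienced a DLT event or received 80% of the expected doses during the DLT period will be included" when dose-level changes are evaluated.
- Section 6.6.3 foresees holds at cycle boundaries: "At the start of each cycle, hold therapy until ANC" and platelets recover to set levels.
- On how long a toxicity delay may last before treatment ends, 6.4 uses more than 28 days, while 6.6.3 and 6.6.5 use more than 21.
- On the five patients treated on the former 3-days-per-week schedule, 9.1.1 says that they are replaced and left out of the analysis. Section 9.2 puts everyone who received a dose into every efficacy and safety set, and 9.4.1 and 9.5.1 put every treated subject into the safety summaries.

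**The concern.** The DLT rate is the phase Ib primary endpoint. It drives Table 8 and the isotonic estimate of the MTD. A criterion that cannot mature before the decision is in practice not applied to that decision, and the plan has no rule for a patient whose hold is still running.

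The criterion is not redundant. Section 4.2.4 counts thrombocytopenia only when it is grade 4 (or a fall of at least 75% from a low baseline) for at least 7 days, or when it comes with grade 3 or higher bleeding, and it exempts grade 3 fatigue. Yet 6.6.3 holds drug for grade 3 thrombocytopenia and 6.6.5 for grade 3 fatigue. For a long hold of that kind, the delay criterion may be the only one that captures the patient. Section 4.1 reports cytopenias as the most common events in the first five patients.

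For those five, two analysts could build different PFS, OS, DoR and safety sets from the same text. The choice shows in the safety tables, because the five include one DLT and two cases of grade 4 thrombocytopenia (4.1).

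**Working it through.** **Plan's own table.** A keyboard rule with a uniform prior and the 25-33% interval of 4.2.1, with U when the posterior probability of a DLT rate above 30% exceeds 0.95 at 3 or more patients (0.95 and 3 are assumptions), reproduces all 75 cells of Table 8 for 1 to 12 patients. The printed table is taken as given below.

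**Timing.** Dosing is 2 days on, 5 days off (6.1). Days 1-2, 8-9 and 15-16 are inferred from the visit and PK calendars; for example, 7.6.3 says "patients will have PK study blood drawn prior to taking their C1D2 and C1D16 drug doses". In elapsed days, a delay first exceeds 21 days on start day + 22.

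| Last dose taken | Counted from last dose | Counted from first missed dose |
|---|---|---|
| Day 1 | 1 + 22 = Day 23 | 2 + 22 = Day 24 |
| Day 2 | 2 + 22 = Day 24 | 8 + 22 = Day 30 |
| Day 9 | 9 + 22 = Day 31 | 15 + 22 = Day 37 |
| Day 16 | 16 + 22 = Day 38 | 22 + 22 = Day 44 |

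Counting the missed day itself as day one moves the last column one day earlier. Every date is after Day 21. A 28-day window would catch only holds that start after the Day 1 or Day 2 dose, and the latter only if counted from the last dose.

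**What happens to the patient.** Cycle 1 has 3 × 2 = 6 dosing days. The 80% rule needs 5 of 6 (83%); 4 of 6 is 67%.
- Held after Day 2 with no other DLT: 2/6 = 33%, so the patient leaves the count under 9.2.1.
- All 6 of 6 taken, then held at Cycle 2 Day 1: the patient is counted as a non-DLT. Section 4.2.4 does not say whether the criterion covers this case.

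**Effect in Table 8.** At n = 3, 6, 9 and 12 there are 3 + 6 + 9 + 12 = 30 cells with at least one DLT. Moving from (x, n) to (x-1, n-1) if the patient is dropped, or to (x-1, n) if counted as a non-DLT, changes these cells:

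| DLT counted | Dropped | Counted as non-DLT |
|---|---|---|
| 1/3 D | 0/2 E | 0/3 E |
| 2/6 D | 1/5 E | 1/6 E |
| 3/9 D | 2/8 S | 2/9 E |
| 3/12 S | 2/11 E | 2/12 E |
| 4/12 D | 3/11 S | 3/12 S |
| 3/3 U | 2/2 D | 2/3 D |
| 4/6 U | 3/5 D | 3/6 D |
| 5/9 U | 4/8 D | 4/9 D |
| 7/12 U | 6/11 U (no change) | 6/12 D |

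This gives 8 changes if dropped and 9 if counted as a non-DLT, all less restrictive. The first five rows change the dose assignment (at 12 patients, S ends phase Ib with that level as the MTD, 4.2.3). The other 3 or 4 are U to D. Both send the next cohort one level down (4.2.2); the difference is that the current level stays open.

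**Table 21.** Condition on 3 or 4 toxicities among 12 rollover patients (within 25-35%), weight by Binomial(12, p), then apply the boundaries from 16 patients on. The crossing probabilities at p = 0.16, 0.20, 0.24, 0.28, 0.32, 0.36 and 0.40 are 13.4, 26.4, 42.4, 58.9, 73.3, 84.3 and 91.7%, against the printed 13.7, 26.3, 41.9, 58.9, 73.3, 84.4 and 91.4%. They agree within 0.5 points, and no window length enters the calculation.

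**Five patients.** Enrolment in 4.4 is phase Ib + 24 - rollover: 12 + 24 - 12 = 24; 18 + 24 - 9 = 33; 18 + 24 - 3 = 39. These totals omit the five, in line with 9.1.1. Only patients treated at the RP2D carry over (4.3), so the five cannot enter the RP2D response rate.

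**The case against.** The strongest reply is that 4.2.4 does not say whether a DLT must begin or be complete inside the window. Other criteria there also depend on duration (neutropenia for 5 days, thrombocytopenia for 7, laboratory recovery within 7), and late-onset cases of these also run past Day 21. Attribution by onset would make them all workable, including the delay criterion. That stands as a possible intent. But no section states it, and none says that the cohort decision waits, so the text as written still lets the decision go first.

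A second reply is that the decision is not automatic. The DSMC and Principal Investigator convene and may use cohorts of 1-2 (4.2.2), the Medical Monitor approves escalations (8.4), and RP2D selection weighs cumulative safety (4.2.3). That limits the practical effect but supplies no rule for a pending hold.

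A reader might infer more than the documents support:
- That every missed delay DLT raises the next dose. It does not: 3 of the 8 changes and 4 of the 9 are U to D.
- That 8/30 or 9/30 is a risk of a wrong decision. The cells are unweighted, and nine of the 30 (6/6, 7-9/9, 8-12/12) cannot be reached in cohorts of 3, because U closes the level first.
- That the 28-day wording invalidates Table 21. The figures reproduce without it.
- That 9.1.1 flatly contradicts the safety rules. It sits under a dose-expansion heading, so it may mean only that analysis. What remains is its scope, and PFS, OS and DoR under 9.2; these are descriptive, without formal testing.

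**Conclusion.** The main point holds. As written, the delay criterion cannot be observed before the decision it should inform, on any of the day counts above, and 9.3 contradicts 4.2.4 on the length of the period. One missed delay DLT changes 8 or 9 of 30 full-cohort cells of Table 8, always in the less restrictive direction, and 5 of them in each case change the dose assignment. How often this would happen cannot be derived: it needs a hold of more than 21 days arising from cycle 1 with no other DLT, and the documents give no rate. The result assumes dosing on Days 1-2, 8-9 and 15-16, cohorts of 3, and completion rather than onset as the test.

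The five-patient conflict is real but smaller. It affects the composition of the PFS, OS, DoR and possibly the safety sets, not the RP2D response rate.

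Two further points are minor clarifications. In 4.2.4, "Subjects will be considered eligible for DLT assessment if they have received at least 1 dose of RP-3500 and 1 dose of olaparib", whereas 9.2.1 accepts a dose of either drug; both start on Day 1, so few patients are affected. And 9.2.1 does not say whether patients below 80% because of a toxicity hold without a DLT are replaced.

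**What to change.** 1. Reconcile 4.2.4, 4.2.2 and 9.3 so that the delay criterion can be observed, or a pending hold resolved, before the cohort decision. State whether DLTs are attributed by onset or by completion, from which day a delay is counted, and whether a delay that starts at Cycle 2 Day 1 is covered. Make the 28-day wording in 9.3 match; Table 21 need not be recalculated.
2. Reconcile the toxicity-delay limits in 6.4 with those in 6.6.3 and 6.6.5. The clinical choice here and in item 1 is the sponsor's.
3. In 9.1.1 and 9.2, state that the five earlier patients are excluded from the keyboard counts, the MTD estimate and the RP2D efficacy analyses (including PFS, OS and DoR), but stay in the safety summaries, labelled by their schedule.
4. As minor clarifications, align the DLT entry rule in 4.2.4 and 9.2.1, and confirm the intent of the 80% rule for patients held for toxicity without a DLT. No change to who is counted is requested.

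The cost is wording and one label in the safety tables. If a pending hold must be resolved first, only the affected cohort decision waits, for about 23 - 21 = 2 to 44 - 21 = 23 days.
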